### **9.5 Efficacy Assessments**

The efficacy of tirzepatide to reduce glucose and weight will be assessed. Efficacy measures that will be assessed include HbA1c, body weight, fasting PG, and 7p-SMPG.

All parameters will be listed and summarized by treatment and timepoint. Changes from baseline will be presented, where baseline is defined as the Day 1 predose assessment (HbA1c, body weight, fasting PG) or the Day -1 assessment (7p-SMPG).

The individual observed and mean time profile of the postdose efficacy parameters will be plotted by treatment group.

## 9.6 Safety and Tolerability Assessments

### 9.6.1 Adverse events

Where changes in severity are recorded in the Case Report Form (CRF), each separate severity of the AE will be reported in the listings, only the most severe will be used in the summary tables. A pre-existing condition is defined as an AE that starts before the subject has provided written informed consent and is ongoing at consent. A non-treatment emergent AE is defined as an AE which starts after informed consent but prior to dosing. A treatment-emergent AE is defined as an AE which occurs postdose or which is present prior to dosing and becomes more severe postdose.

All AEs will be listed. Treatment-emergent AEs will be summarized by treatment, severity and relationship to the study drug. The frequency (the number of AEs, the number of subjects experiencing an AE and the percentage of subjects experiencing an AE) of treatment-emergent AEs will be summarized by treatment, Medical Dictionary for Regulatory Activities (MedDRA) version 22.1 system organ class and preferred term. The summary and frequency AE tables will be presented for all causalities and those considered related to the study drug by the investigator. Any serious AEs will be listed. AEs by week of onset will be presented.

Discontinuations due to AEs will be listed.

### 9.6.2 Glucose Monitoring and Hypoglycemia

Hypoglycemic events will be appropriately recorded in the CRF. In the case of a hypoglycemic event, the actual blood glucose value, if measured, will be recorded in the CRF, together with any treatments administered. Each category of hypoglycemic events (defined below) will be listed and summarized by treatment. Hypoglycemia is defined as follows:

- **Documented Glucose Alert Level (Level 1), PG  $\leq 70$  mg/dL (3.9 mmol/L):**
  - **Symptomatic hypoglycemia:** an event during which typical symptoms of hypoglycemia are accompanied by PG  $\leq 70$  mg/dL (3.9 mmol/L)
  - **Asymptomatic hypoglycemia:** an event not accompanied by typical symptoms of hypoglycemia but with PG  $\leq 70$  mg/dL (3.9 mmol/L)
  - **Unspecified hypoglycemia:** an event during which PG  $\leq 70$  mg/dL (3.9 mmol/L) but no information relative to symptoms of hypoglycaemia was recorded
- **Documented Clinically Significant Hypoglycemia (Level 2) PG  $\leq 54$  mg/dL (3.0 mmol/L):**
  - **Symptomatic hypoglycemia:** an event during which typical symptoms of hypoglycemia are accompanied by PG  $\leq 54$  mg/dL (3.0 mmol/L)
  - **Asymptomatic hypoglycemia:** an event not accompanied by typical symptoms of hypoglycemia but with PG  $\leq 54$  mg/dL (3.0 mmol/L)

- **Unspecified hypoglycemia:** an event during which PG  $\leq 54$  mg/dL (3.0 mmol/L) but no information relative to symptoms of hypoglycemia was recorded.
- **Severe hypoglycemia (Level 3):** an event requiring the assistance of another person to actively administer carbohydrate, glucagon, or other resuscitative actions. During these episodes, the subject has an altered mental status and cannot assist in their care, is semiconscious or unconscious, or experienced coma with or without seizures and may require parenteral therapy. Plasma glucose measurements may not be available during such an event, but neurological recovery attributable to the restoration of blood glucose concentration to normal is considered sufficient evidence that the event was induced by a low PG concentration ( $\leq 70$  mg/dL [3.9 mmol/L]).
  - **Severe hypoglycemia requiring medical attention:** a severe hypoglycemic event when subjects require therapy by health care providers (emergency medical technicians, emergency room personnel, etc.).

### **Other Hypoglycemia:**

- **Nocturnal hypoglycemia:** any hypoglycemic event (documented symptomatic, asymptomatic, probable symptomatic, or severe hypoglycemia) that occurs between bedtime and waking
- **Relative hypoglycemia:** an event during which typical symptoms of hypoglycemia, which do not require the assistance of another person, are accompanied by PG  $>70$  mg/dL (3.9 mmol/L), but these levels may be quickly approaching the 70 mg/dL (3.9 mmol/L) threshold
- **Overall (or total) hypoglycemia:** this optional category combines all cases of hypoglycemia. If an event of hypoglycemia falls into multiple subcategories, the event is counted only once in this category
- **Probable symptomatic hypoglycemia:** an event during which symptoms of hypoglycemia are not accompanied by a PG measurement but that was presumably caused by PG  $\leq 70$  mg/dL (3.9 mmol/L).

Investigator review of glucose results clinically indicative of hypoglycemia will be required.

#### **9.6.3 Concomitant medication**

Concomitant medication will be coded using the WHO drug dictionary (Version September 2019). Concomitant medication will be listed.

#### **9.6.4 Clinical laboratory parameters**

All clinical chemistry and hematology data will be summarized by parameter, treatment, and timepoint together with changes from baseline, where baseline is defined as the Day -1 assessment. All clinical chemistry, hematology and urinalysis data will be listed.

Additionally, clinical chemistry, hematology and urinalysis data outside the reference ranges will be listed and flagged on individual subject data listings.

### **9.6.5 Pancreatic Enzymes**

Pancreatic amylase and lipase will be measured to monitor pancreatic safety. All parameters will be listed and summarized by parameter and treatment together with changes from baseline, where baseline is defined as the Day -1 assessment. Data outside the reference range will also be listed and flagged on individual subject data listings.

### **9.6.6 Thyroid Malignancies and C-Cell Hyperplasia**

The assessment of thyroid safety during the trial will include reporting of any case of thyroid malignancy including medullary thyroid carcinoma and papillary carcinoma and measurements of calcitonin.

Calcitonin data will be summarized by treatment and timepoint together with changes from baseline, where baseline is defined as the Day 1 predose assessment.

### **9.6.7 Vital signs**

Vital signs data will be summarized by treatment together with changes from baseline, where baseline is defined as the Day 1 predose assessment. Figures of mean vital signs and mean changes from baseline profiles will be presented by treatment.

Values for individual subjects will be listed.

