explore alternative titration schemes (longer time intervals between dose escalations and different dose escalations) to support evaluation of optimised dosing regimen(s) in Phase 3. Study GPGF demonstrated that a longer time between dose increases and/or smaller dose escalations are better tolerated than rapid or large step-size dose escalations, as indicated by lower frequency of GI tolerability AEs and fewer patients discontinuing treatment compared to the data observed in Study GPGB.

In addition, the safety, tolerability, and PK/PD of tirzepatide are being evaluated in the ongoing Study GPGC; a Phase 1, 8-week multiple ascending dose (MAD) study in Japanese patients with T2DM. This study involves a comparison of 3 once-weekly SC dose levels of tirzepatide (2.5 mg to 10 mg titration regimen for Cohort 1; 5 mg to 15 mg titration regimen for Cohort 2; and 5 mg fixed dose for Cohort 3), or placebo. The safety and tolerability data of Study GPGC supports the use of doses up to 15 mg of tirzepatide in Japanese patients.

Tirzepatide PK was studied across a range of doses administered as single doses or multiple doses via a once-weekly dosing regimen. Based on the cumulative data to date, tirzepatide PK appeared linear and dose proportional during the dose range studied. Peak concentrations were observed at 1 to 2 days postdose, and the half-life was approximately 5 days.

In summary, the data from Study GPGB and Study GPGF support continued development of tirzepatide as a treatment for T2DM. Lilly proposes to conduct five Phase 3 randomised, controlled glycaemic-control trials. The doses selected for this study are 2.5, 5, 7.5, 10, 12.5, and 15 mg, which will be administered in a dose-escalation scheme that uses 2.5-mg dose increments and 4-week intervals.

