### 3.3. Benefit/Risk Assessment

To minimize the risk of hyperglycemia due to the washout of prestudy oral antidiabetic medication, patients will monitor their fasting glucose levels using self-monitored plasma glucose (SMPG). Episodes of hyperglycemia will be reported and managed by the investigator or designated physician (Section 9.4.4.1).

Because tirzepatide is a long-acting, GIP and GLP-1 receptor dual agonist, the potential risks associated with tirzepatide may be similar to the risks associated with other long-acting GLP-1 receptor agonists. The known risks associated with increased GLP-1 receptor activity include but are not limited to GI-related adverse reactions (particularly nausea, vomiting, and diarrhea), pancreatitis, cardiovascular risk (increased heart rate), hypoglycemia, systemic allergic reaction, injection-site reactions, antibody formation, and medullary thyroid carcinoma (MTC). In previous tirzepatide Phase 1 and Phase 2 studies, the observed AEs were consistent with that of other GLP-1 agonists.

More information about the known and expected benefits, risks, SAEs, and reasonably anticipated AEs of tirzepatide is to be found in the Investigator's Brochure (IB).

More information about the known risks for the QW GLP-1 receptor agonists can be found in the Bydureon® ([exenatide extended-release] for injectable suspension) package insert (Astra Zeneca 2018, China).

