#### **10.3.1.2. Statistical Evaluation of Safety**

Safety parameters that will be assessed include safety laboratory parameters, vital signs, ECG parameters, injection-site reactions, and hypoglycemia. The parameters will be listed and summarized using standard descriptive statistics. Additional analysis will be performed if warranted upon review of the data.

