### **9.6.8 Electrocardiogram (ECG)**

ECGs will be performed for safety monitoring purposes only and will not be presented. Any clinically significant findings from ECGs will be reported as an AE.

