## **11. CHANGES FROM THE PROTOCOL SPECIFIED STATISTICAL ANALYSES**

There were no changes from the protocol specified statistical analyses.

---

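### Above 2.5 mg, pulse and blood pressure are scheduled only at trough and the SAP drops the ECGs taken 24 to 72 h after the last dose, so no planned output can show the peak-window heart-rate effect at 10 or 15 mg

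*SAP*

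**What the plan says.** **Schedule (Protocol section 2, treatment-period tables).** In both cohorts the Vital Signs (BP/PR) row has readings predose and at 2, 4, 8, 24, 48 and 72 h around the Day 1 dose of 2.5 mg. Later treatment entries are predose, or fall at the end-of-treatment visit (Day 113 in Cohort 1, Day 169 in Cohort 2), 7 days after the last dose. There are also later follow-up and early-discontinuation readings. The 12-lead ECG row in the same tables does carry 24, 48 and 72 h after the last dose (Day 106 at 10 mg, Day 162 at 15 mg), while patients are inpatients.

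**Pharmacology (Protocol 3.2 and 3.3).** "Peak concentrations were observed at 1 to 2 days postdose, and the half-life was approximately 5 days". Over the doses studied, "tirzepatide PK appeared linear and dose proportional during the dose range studied". Section 3.3 names increased heart rate among the known risks of GLP-1 receptor activity.

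**Vital-sign analysis (SAP 9.6.7).** "Vital signs data will be summarized by treatment together with changes from baseline, where baseline is defined as the Day 1 predose assessment". The figures are described only by "Figures of mean vital signs and mean changes from baseline profiles will be presented by treatment". Nothing separates near-peak readings from trough readings.

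**ECG analysis.** SAP 9.6.8: "ECGs will be performed for safety monitoring purposes only and will not be presented". Protocol 10.3.1.2: "Safety parameters that will be assessed include safety laboratory parameters, vital signs, ECG parameters, injection-site reactions, and hypoglycemia". The next sentence there says that these parameters will be listed and summarized. SAP section 11: "There were no changes from the protocol specified statistical analyses".

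**The concern.** Safety and tolerability is the primary objective, and Protocol 5.5 says the study should inform benefit and risk at 10 and 15 mg. Heart rate is a named risk. Yet the window in which concentration peaks is covered by pulse readings only at the lowest dose. At every higher dose the scheduled on-treatment readings sit at the low point of the weekly cycle.

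The one scheduled source of near-peak heart rate at the target doses is the set of ECGs after the last dose, and the SAP leaves these out of the outputs. A reader of the study report could take the vital-sign figures as the full heart-rate picture at 10 and 15 mg when they show only the trough.

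**Working it through.** The plan states no heart-rate effect size, standard deviation or power, so there is no figure of its own to reproduce. The question is how far trough lies below peak at the final dose, and what that means for pulse.

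**Inputs from the documents.** Half-life 5 days, single-dose tmax 1 to 2 days, linear PK (Protocol 3.2). Weekly doses, four per step: 2.5/5/7.5/10 mg (Cohort 1) and 2.5/5/7.5/10/12.5/15 mg (Cohort 2).

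**Assumed model.** One compartment with first-order absorption, superposed over all doses:

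- C(t) = Σ Dᵢ · ka/(ka − ke) · [exp(−ke(t − tᵢ)) − exp(−ka(t − tᵢ))], summed over doses already given
- ke = ln 2 / 5 = 0.1386 per day
- ka solves ln(ka/ke)/(ka − ke) = tmax

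**Worked case, tmax 1.5 days.** ka = 1.875 per day. In dose/volume units the first-dose peak is 2.5 × exp(−0.1386 × 1.5) = 2.031.

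- Cohort 1, last 10 mg dose: predose 6.497, peak 13.508; ratio 6.497/13.508 = 0.48.
- Cohort 2, last 15 mg dose: predose 9.791, peak 20.301; ratio 9.791/20.301 = 0.48.

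**Range over tmax (half-life 5 days).**

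| Quantity at the last dose | tmax 1 d | tmax 1.5 d | tmax 2 d |
|---|---|---|---|
| Predose / peak | 0.44 | 0.48 | 0.53 |
| 168 h / peak | 0.45 | 0.49 | 0.53 |
| 24 h / peak | 1.00 | 0.99 | 0.96 |
| 48 h / peak | 0.89 | 0.95 | 0.99 |
| 72 h / peak | 0.77 | 0.84 | 0.90 |
| Predose / first-dose peak, Cohort 1 | 2.89 | 3.20 | 3.58 |
| Predose / first-dose peak, Cohort 2 | 4.35 | 4.82 | 5.39 |

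The first five rows agree between cohorts to about 0.01. With half-life varied over 4 to 6 days, trough/peak runs from 0.37 to 0.58.

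**From concentration to pulse.** The documents give no exposure-response relation, so three assumed forms are shown. The last two use tmax 1.5 days and the predose ratio r = 0.481.

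- Linear, no delay: trough shows the same share as concentration, 44-53% of the peak effect.
- Saturable (Emax), EC50 = f × peak: share = r(1 + f)/(r + f). For f = 0.25, 0.5, 1 and 2 this gives 82%, 74%, 65% and 58%.
- Delayed effect, dE/dt = k(C − E), with k = ln 2 / delay half-life. Delays of 0.5, 1, 3 and 7 days give about 57%, 67%, 85% and 92%.

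**Precision.** With 10 tirzepatide and 4 pooled placebo patients, the 95% half-width is 2.179 × SD × √(1/10 + 1/4). For an assumed SD of change of 6, 8 or 10 bpm this is 7.7, 10.3 or 12.9 bpm.

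**ECG reporting, side by side.** Protocol 10.3.1.2 lists and summarizes ECG parameters. SAP 9.6.8 presents none. SAP section 3 says the SAP supersedes the protocol's statistical considerations and that substantial differences will be identified. SAP section 11 identifies none.

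**The case against.** A reader might infer that the planned figures understate any heart-rate rise, or flatten a dose-related rise by design. The documents do not support that. The predose series is on one consistent basis. In the model, trough concentration climbs from 0.45-0.56 of the first-dose peak on Day 8 to 2.9-3.6 times it before the last 10 mg dose and 4.4-5.4 times it before the last 15 mg dose. A concentration-driven rise would therefore still appear, and the trough change is measured directly. Only the within-week peak is out of view.

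Further points for the sponsor:

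- The figure of one half needs a linear, immediate effect. Nothing in the documents establishes that pulse tracks concentration within the week. This stands, and the size is conditional.
- Peak-window cardiac monitoring does take place. ECGs are read by a physician, clinically significant findings become adverse events, and extra vital signs may be taken if warranted (Protocol 9.4.2 and 9.4.3). This protects the individual patient, but it gives no summary of heart rate by treatment.
- SAP 9.6.7 does not say that predose and postdose readings will be joined in one line, and the table and figure shells are a separate document. This stands: the layout is unspecified, not shown to be wrong.
- The primary endpoint is the incidence of treatment-emergent adverse events, the analysis is descriptive, and the precision above is poor. Three more readings will not make the estimate precise. They would give the report a peak-window reading at the target doses, which it otherwise lacks.
- Table columns are misaligned in the text reviewed, most of all in Cohort 2, so not every predose entry can be tied to a visit. Neither vital-sign row shows a postdose hour after Day 4.

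**Conclusion.** The point holds in limited form. No planned output covers heart rate in the peak window at 10 or 15 mg, because the vital signs above 2.5 mg are trough readings and the ECGs that cover the window are not presented. The omission of ECG results conflicts with Protocol 10.3.1.2 and is not declared in SAP section 11.

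The outputs may understate the peak effect; they do not hide a rise at trough. Trough readings would show roughly half of the peak effect under a linear, undelayed response, and about 57-92% under the alternatives tried. These percentages rest on an assumed one-compartment model and assumed response forms. The schedule gap and the conflict over ECG reporting rest on the documents alone. This is an inexpensive improvement to a study whose primary objective is safety, not a flaw that invalidates its results.

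**What to change.** 1. **Protocol section 2.** Add supine BP and pulse at 24, 48 and 72 h after the Day 106 dose (Cohort 1) and the Day 162 dose (Cohort 2), alongside the ECGs already scheduled. In the model these times fall at 96-100%, 89-99% and 77-90% of peak concentration.
2. **SAP 9.6.8.** In addition, or instead if the schedule cannot change, list and summarize heart rate from those ECGs by treatment and timepoint. This needs no new procedure, provided ECG heart rate is entered in the database, which the documents do not state. Reconcile SAP 9.6.8 with Protocol 10.3.1.2; if ECG results stay out, declare it in SAP section 11.
3. **SAP 9.6.7.** Plot predose readings across dose steps as one display, labelled as trough. Show postdose readings separately, comparing the first and final dose at the same hours after dosing.

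The cost is three short readings per patient within an existing inpatient stay, an amended schedule row, a few SAP sentences and slightly more analysis work.

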### **9.6.8 Electrocardiogram (ECG)**

ECGs will be performed for safety monitoring purposes only and will not be presented. Any clinically significant findings from ECGs will be reported as an AE.

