**Statistical Analysis:**

Pharmacokinetics, PD, and efficacy analyses will be conducted on data from all patients who receive at least 1 dose of the IP and have evaluable PK, PD, and efficacy data. Safety analyses will be conducted for all enrolled patients, whether or not they completed all protocol requirements.

**Safety:** All IP and protocol procedure-related adverse events will be listed, and if the frequency of events allows, safety data will be summarized using descriptive methodology. Safety parameters that will be assessed include safety laboratory parameters, vital signs, electrocardiogram parameters, injection-site reactions, and hypoglycemia.

**Efficacy:** The efficacy of tirzepatide to reduce glucose and weight will be assessed. All parameters will be listed and summarized using standard descriptive statistics.

**Pharmacodynamics:** Lipids and subjective appetite sensation (VAS) will be listed and summarized using descriptive methodology.

**Pharmacokinetics:** The primary parameters for analysis will be maximum drug concentration ( $C_{max}$ ), area under the concentration-time curve (AUC), and time to  $C_{max}$  ( $T_{max}$ ) of tirzepatide. Other noncompartmental parameters, such as half-life, apparent clearance, and apparent volume of distribution may be reported. Pharmacokinetic parameters will be summarized using descriptive statistics. The mean concentration-time profiles in linear and semilog scale for each tirzepatide-treated group will be presented.

**Immunogenicity:** The frequency and percentage of subjects/patients with preexisting antidrug antibodies (ADAs) and with treatment-emergent (TE) ADA to tirzepatide will be tabulated. The frequency of neutralizing antibodies to tirzepatide and/or cross-reactive to endogenous counterparts may also be tabulated in TE ADA patients.

The relationship between the presence of antibodies, antibody titres, and clinical parameters (for example, AEs) may be assessed. Likewise, the relationship between antibody titers, PK parameters, and PD response to tirzepatide may be assessed.

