## **Overview**

Protocol I8F-MC-GPHT, A Multiple Dose Titration Study in Chinese Patients with Type 2 Diabetes Mellitus to Investigate the Safety, Tolerability, Pharmacokinetics, Pharmacodynamics, and Efficacy of Tirzepatide, has been amended. The new protocol is indicated by Amendment (b) and will be used to conduct the study in place of any preceding version of the protocol.

This amendment is not considered a substantial protocol amendment.

The overall changes and rationale for the changes made to this protocol are as follows:

- Single-site has been removed from the study design because more than one site may be used for screening and enrollment in this study.
- The appendix referenced in Section 9.4.4.1 Hepatic Safety has been corrected to Appendix 4.

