### **3. INTRODUCTION**

This SAP has been developed after review of the Clinical Study Protocol (final version dated 13 March 2019) and Protocol Amendment (a) (final version dated 14 February 2020).

This SAP describes the planned analysis of the safety, tolerability, pharmacokinetic (PK), pharmacodynamic (PD), and efficacy data from this study. A detailed description of the planned TFLs to be presented in the clinical study report (CSR) is provided in the accompanying TFL shell document.

The intent of this document is to provide guidance for the statistical and PK analyses of data. In general, the analyses are based on information from the protocol, unless they have been modified by agreement with Eli Lilly and Company. A limited amount of information concerning this study (e.g., objectives, study design) is given to help the reader's interpretation. When the SAP and TFL shells are agreed upon and finalized, they will serve as the template for this study's CSR.

This SAP supersedes the statistical considerations identified in the protocol; where considerations are substantially different, they will be so identified. If additional analyses are required to supplement the planned analyses described in this SAP, they may be performed and will be identified in the CSR. Any substantial deviations from this SAP will be agreed upon with Eli Lilly and Company and identified in the CSR. Any minor deviations from the TFLs may not be documented in the CSR.

This SAP is written with consideration of the recommendations outlined in the International Conference on Harmonisation (ICH) E9 Guideline entitled Guidance for Industry: Statistical Principles for Clinical Trials and the ICH E3 Guideline entitled Guidance for Industry: Structure and Content of Clinical Study Reports.

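### SAP 9.6.8 drops the ECG listing and summary that Protocol 10.3.1.2 specifies, while SAP 11 declares no changes from the protocol analyses

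*SAP*

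**What the plan says.** Protocol 10.3.1.2 (Statistical Evaluation of Safety) sets the scope: "Safety parameters that will be assessed include safety laboratory parameters, vital signs, ECG parameters, injection-site reactions, and hypoglycemia". The next sentence says what will be done with them: "The parameters will be listed and summarized using standard descriptive statistics". The protocol synopsis, under Statistical Analysis, names the same five groups.

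SAP 9.6.8 says of the ECG: "ECGs will be performed for safety monitoring purposes only and will not be presented". It adds that clinically significant ECG findings will be reported as adverse events.

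Two further SAP sections govern how such a difference should be handled. SAP 3: "This SAP supersedes the statistical considerations identified in the protocol; where considerations are substantially different, they will be so identified". SAP 11: "There were no changes from the protocol specified statistical analyses".

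SAP 9.1 also bears on the point. It promises a data listing for everything held in the database and limits summaries to what the SAP details.

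**The concern.** The two documents give opposite instructions for the same data, and the section meant to record such differences says there are none. A programmer following the SAP would produce no ECG table. A reader of the study report who relies on SAP 11 would believe that the protocol's safety analysis had been carried out in full.

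Safety and tolerability is the primary objective (Protocol 4). Under SAP 9.6.8, ECG results are reported through findings that an investigator has judged clinically significant. That judgement is made patient by patient. If most patients on a regimen moved modestly in the same direction and none crossed the line of clinical significance, no summary would show it. Descriptive tables by treatment group exist to show that kind of pattern.

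**Working it through.** No arithmetic is needed beyond a count. The check compares the five groups in Protocol 10.3.1.2 with the output that the SAP plans for each.

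| Group named in Protocol 10.3.1.2 | SAP section | Planned output |
|---|---|---|
| Safety laboratory parameters | 9.6.4 | Chemistry and hematology summarized and listed; urinalysis listed only |
| Vital signs | 9.6.7 | Summarized, plotted and listed |
| Injection-site reactions | 9.6.12 | Summarized and listed |
| Hypoglycemia | 9.6.2 | Summarized and listed |
| ECG parameters | 9.6.8 | None |

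Four of five groups have output; 5 − 4 = 1 has none.

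Four explanations could remove the conflict. Each was checked.

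1. *Is the protocol's commitment conditional?* No. The condition about the frequency of events stands in Protocol 10.3.1.1, which deals with adverse events. The listing-and-summary sentence in 10.3.1.2 has no condition.

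2. *Does another part of the SAP supply the output?* Not the summary: SAP 9.1 confines summaries to what the SAP details, and 9.6.8 details none. For listings, SAP 9.6.13 lists safety assessments that the SAP does not otherwise cover, but ECG is covered, in 9.6.8. SAP 9.1 promises listings of all data in the database. If ECG values are there, 9.1 and 9.6.8 contradict each other; if they are not, nothing would be listed. The documents do not say which applies.

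3. *Does the SAP's precedence settle it?* It settles which text governs, but the same sentence in SAP 3 says substantial differences will be identified. No section of the SAP identifies this one, and SAP 11 says there were none.

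4. *Is it a version difference?* No. SAP 3 states that the SAP was written after review of the protocol and Amendment (a). The protocol reviewed here is Amendment (b), whose Appendix 6 gives two changes. One is: "Single-site has been removed from the study design because more than one site may be used for screening and enrollment in this study". The other corrects an appendix reference in the hepatic safety section. Neither concerns ECG or Section 10.3.1.2.

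The conflict remains after all four checks.

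**The case against.** The strongest reply is that little of consequence is lost. The primary endpoint is the incidence of treatment-emergent adverse events, and clinically significant ECG findings still enter it. Pulse rate is part of vital signs in the Schedule of Activities and is summarized and plotted under SAP 9.6.7. No inferential safety analysis is planned (SAP 9.6.14), and the sample size rests on no statistical requirement (Protocol 10.1). With about 10 patients per tirzepatide regimen and 2 + 2 = 4 pooled placebo patients, a descriptive table might not reveal a modest shift. SAP 3 does not define a substantial difference, so the sponsor could argue that this one falls short.

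Most of this stands, and it limits the size of the point. It does not remove it. Protocol 10.3.1.2 asks for ECG parameters in addition to the adverse event reporting in 10.3.1.1, so adverse event capture is not a substitute. Removing all planned output for a named safety group, where safety is the primary objective, is hard to call insubstantial. Whatever view is taken of that word, the statement in SAP 11 is unqualified and inaccurate.

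A reader might infer more than the documents support:

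- *That ECG data can reach the report only through adverse events.* This is too firm, because SAP 9.1 may still require listings.
- *That a known number of recordings is lost.* No count is reliable. The schedule rows are broken in the text available, and Protocol 9.4.3 refers to replicate ECGs, so recordings per time point are uncertain.
- *That ECG is the only heart-rate record near peak exposure at the top dose.* This would depend on the same broken rows.
- *That the loss is specifically PR, QRS or QT data.* The protocol does not define ECG parameters. Its PR limit is an entry criterion, and its mention of QT change concerns patient management; neither is an analysis commitment.

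**Conclusion.** The point holds as an undeclared departure from the protocol's safety analysis. One of five named safety parameter groups has no planned output, and SAP 11 is wrong to declare no changes. The certain loss is the descriptive summary of ECG parameters; the fate of the listings depends on whether ECG values are in the database. The primary endpoint definition and the adverse event analysis are unaffected, and nothing suggests that significant findings would go unreported.

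This should be fixed, but it does not threaten the validity of the trial. The conclusion rests on the text alone and needs no assumption about effect size, variability or the number of ECGs recorded.

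**What to change.** Replace SAP 9.6.8 with wording such as: *ECG parameters will be listed and summarized by treatment and timepoint using descriptive statistics. Clinically significant findings will also be reported as AEs.* Naming the intervals and adding change from Day 1 predose, on the model of SAP 9.6.7, would be useful but is optional; the protocol does not require either.

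The cost is one listing and one table, with no new patient procedures. If ECG values are not in the database, they would have to be entered from the recordings that Protocol 9.4.3 tells sites to store. The sponsor should establish this first, since it also settles how SAP 9.1 applies.

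If the sponsor prefers to keep the omission, SAP 11 must be corrected, for example: *Protocol 10.3.1.2 specifies that ECG parameters will be listed and summarized; this SAP does not present them because [reason].* That costs one sentence. It makes the record accurate but does not recover the summary.
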